### **10.4 Assessments of safety**

#### ***Safety endpoint:***

8. Proportion of patients with common adverse events (reported in greater than 5%).
9. Proportion of patients with at least one severe or potentially life threatening (grade 3 or 4) adverse event.
10. Proportion of patients with un-scheduled clinic visits.

Safety analyses will also be undertaken with the proportion of patients with Grade 3 or 4 adverse events, and grade adverse events will be summarised by randomised treatment group, by severity and relation to study drug. Serious adverse events will be summarised for all enrolled patients.

### **10.5 Definition of Intent-to-treat Population**

Intent-to-treat (ITT) and modified intent-to-treat (mITT) populations will be used for efficacy analyses. All patients who receive at least one dose of study drug will be included in the ITT population (and safety population). The mITT population will exclude patients who have completed treatment (>95% adherence) (according to phone contact at week 8), but have not returned for their SVR12 assessment. The data from the ITT and mITT will be presented by the treatment arm assigned at the time of randomisation. For the primary analyses of non-inferiority tests, the percentage of patients achieving SVR12 in each arm will be calculated with confidence intervals (CI) using the normal approximation to the binomial distribution.

### **10.6 Definition and evaluation of HCV resistance**

Regions encoding NS3 and NS5A will be sequenced from available baseline samples from all patients, and from the first available post-baseline sample with HCV RNA  $\geq 1000$  IU/mL from patients with virologic failure. Baseline polymorphisms relative to a subtype-specific reference sequence for all patients, and

treatment-emergent substitutions relative to the patient's baseline sequence for patients with virologic failure will be identified using the following set of amino acid positions: 36, 43, 54, 55, 56, 80, 155, 156, 166, 168 in NS3; 24, 28, 29, 30, 31, 32, 58, 92, 93 in NS5A. These are positions at which substitutions have been observed in vitro or clinically in NS3 or NS5A in any genotype with drugs for the respective inhibitor class.

### **11.0 Data Safety and Monitoring Board (DSMB)**

A data safety and monitoring board (DSMB) will consist of at least 1 statistician and 2 practicing gastroenterologist/infectious diseases specialists. The meeting will include the interim safety and adherence analysis which will be performed when the first 75 participants have either completed SVR12 or dropped out of the study. Additional DSMB meetings will be scheduled at a frequency commensurate with the risk as determined by the DSMB.

### **12.0 Data collection, source documents and record retention**

The Principal Investigator and the institution where the study will be conducted will permit study-related monitoring, audits, ethics committee review and regulatory inspection providing direct access to source documents.

Data will be collected on study specific electronic or paper copy case record forms. The Principal Investigator is responsible for ensuring the data collected are complete, accurate and recorded in a timely manner.

#### **12.1 Submission of data**

Electronic CRFs: following each participant visit the designated site staff will complete the visit specific eCRF. Once all required information is received the eCRF shall be considered complete. Project Team staff will then monitor the data for completeness and accuracy. Any eCRF discrepancies, either manual or automatic, will be addressed with the site staff for clarification.

The site Principal Investigator is responsible for ensuring the completion of accurate source documentation to support data collected on case report forms. Source documents include all recordings of observations or notations of clinical activities and all reports and records necessary for the evaluation and reconstruction of the trial. Source documents include, but are not limited to; participant medical records, laboratory reports, ECG tracings, X-rays, radiologist reports, participant diaries, biopsy reports, ultrasound images, participant progress notes, pharmacy records and any other reports or records of procedures performed in accordance with the protocol.

It is not acceptable for the CRF to be the only record of study participation and progress must also be recorded in the each person's medical record. This is to ensure that anyone accessing the medical record has adequate knowledge that the person is a clinical trial participant.

Any document that acts as a source document (the point of the initial recording of a piece of data) should be signed and dated by the person recording or reviewing the data for issues of medical significance (for example the review of laboratory reports). Persons signing the source documents must be listed as a site staff member.

The sponsor's monitor will visit sites to conduct source document verification. The number of visits will depend upon study complexity and recruitment rate; however, the monitor will conduct a minimum of three source data verification visits during the study. Ideally the first will occur shortly after randomisation of the first participant(s), the second during study conduct and the final following completion of all study visits. Additional monitoring visits may be scheduled if required.

The Principal Investigator is responsible for retaining all essential documents listed in ICH Good Clinical Practice guidelines. These must be organised in a comprehensive filing system that is accessible to study monitors and other relevant personnel.

## **12.2 Archiving**

The Principal Investigator is responsible for ensuring all study documents are retained for a minimum of 15 years following completion and publication of the study or for the duration required by the local regulatory authority.

## **13.0 Ethics committee/regulatory approval and informed consent**

The sponsor is responsible for ensuring regulatory approval for the study is obtained.

The site Principal Investigator is responsible for obtaining IRB/EC approval for the protocol and participant information and informed consent form in compliance with local regulatory requirements prior to entering any participant into the study. The approval letter/document must clearly identify the protocol and all documents approved by the IRB/EC including version number & date of the protocol and participant information and consent form. A copy of the approval document must be sent to the study sponsor.

The site Principal Investigator must also obtain approval for any amendments to the protocol or participant information and informed consent form. The Principal Investigator must comply with all IRB/EC reporting requirements for all adverse events, annual updates and end of study reports and must agree to abide by any IRB/EC conditions of approval.

The site Principal Investigator (or designee) is responsible for ensuring freely-given consent is obtained from each potential participant prior to the conduct of any protocol-specific procedures. The Principal Investigator may delegate the task of obtaining consent to appropriately qualified Sub-investigator(s). Consent must be documented by the participant's dated signature on the participant information and consent form together with the dated signature of the person conducting the consent discussion.

A copy of the signed and dated participant information and consent form must be given to the person prior to study participation. The participant or their legally authorised representative must be informed in a timely manner of any new information that becomes available during the course of the study that may affect his/her willingness to continue study participation.

This study shall be conducted in accordance with the ethical principles laid out in the Declaration of Helsinki (most current issued version) and the National Statement on Ethical Conduct in Research Involving Humans (most current issued version).

## **14.0 Confidentiality of data**

### **14.1 Confidentiality of participant records**

By signing the Clinical Trial Agreement, the site Principal Investigator agrees that the sponsor, IRB/EC or regulatory authorities may consult and/or copy study documents to verify information in the case report form. By signing the consent form the participant agrees to these processes.

Participant confidentiality will be maintained at all times and no documents containing the participant's name or other identifying information will be collected by the sponsor. It may be necessary for the sponsor's representatives, the IRB/EC and regulatory authority representatives to have direct access to the participant's medical records. If study documents need to be photocopied during the process of verifying case report form data, the participant will be identified by a unique code only; full names and other identifying information will be masked.

### **14.2 Confidentiality of study data**

By signing the Clinical Trial Agreement, the site Principal Investigator affirms to the sponsor that information provided to them by the sponsor will be maintained in confidence and divulged only as necessary to the ethics committee and institution employees directly involved in the study. Both ethics committee members and employees must also understand the confidentiality requirements for any information divulged to them. The data generated by this study will be considered confidential, except where it is included in a publication as agreed in the publication policy of this protocol.

At sites where regulations restrict the collection of full date of birth and/or initials, the following conventions will be used:

- Date of birth will be entered as 01/01/YYYY
- Initials will be entered as AA-AA, BB-BB, CC-CC etc.

### **15.0 Governance**

This research protocol is sponsored by UNSW Sydney with funding and provision of study drug by AbbVie Pty LTD. The study is coordinated through the Kirby Institute for Infection and Immunity in Society, UNSW Australia. The Kirby Institute has established governance and implementation structures which use resources efficiently to deliver program objectives on schedule.

### **16.0 Quality Control (QC) and Quality Assurance (QA)**

The sponsor agrees to be responsible for implementing and maintaining quality control and quality assurance systems with written standard operating procedures to ensure the study is conducted and data are generated, documented and reported in compliance with the protocol, Good Clinical Practice standards and all applicable local laws and regulations relating to the conduct of a clinical trial.

### **17.0 Publication Policy**

The results of this study may be published and presented at scientific meetings. Publication of data derived from this protocol will be governed by the Protocol Steering Committee. All published data will be non-identifiable grouped data and will follow the guidelines set forth by the International Committee of Medical Journal Editors (ICMJE).

## 19.0 Abbreviations List

ACD	Acid Citrate Dextrose
AE	Adverse Event
ALT	Alanine Aminotransferase
APRI	AST to Platelet Ratio Index
ART	Antiretroviral Therapy
AST	Aspartate Aminotransferase
CI	Confidence interval
DAA	Direct Acting Antiviral
EC	Ethics Committee
eCRF	Electronic Case Report Form
EDTA	Ethylenediamine Tetraacetic Acid
EOT	End of Treatment
FBC	Full Blood Count
FPFV	First Patient First Visit
GGT	Gamma Glutamic Transpeptidase
HBC	Hepatitis B Virus
HCV	Hepatitis C Virus
Hgb	Haemoglobin
HIV	Human Immunodeficiency Virus
INR	International Normalized Ratio
IRB	Institutional Review Board
ITT	Intent-to-treat
IUD	Intrauterine device
IUS	Intrauterine hormone-releasing system
LFTs	Liver Function Tests
LLN	Lower Limit of Normal
LLOQ	Lower Limit Of Quantification
LPLV	Last Patient Last Visit
mITT	Modified intent-to treat
PEG-IFN	Pegylated interferon alfa 2a/b
PBMC	Peripheral Blood Mononuclear Cell
RAS	Resistance Associated Substitutions
SAE	Serious Adverse Event
SUSAR	Suspected Unexpected Serious Adverse Reaction
SVR12	Sustained Virological Response (HCV RNA undetectable 12 weeks post-treatment)
UDS	Urinary Drug Screen
ULN	Upper Limit of Normal
UNSW	University of New South Wales
WCC	White Cell Count
WOCBP	Women of Childbearing Potential

## LIST OF ABBREVIATIONS

AE	adverse event
ALT	alanine aminotransferase
APRI	AST:platelet ratio index
APTT	activated partial thromboplastin time
ARV	antiretroviral
AST	aspartate aminotransferase
BLoQ	below the lower limit of quantitation
cART	combination antiretroviral therapy
CI	confidence interval
CPT	Child-Pugh-Turcotte
DAA	direct acting antiviral
ECG	electrocardiogram
eCRF	electronic case report form
EOT	end of treatment
FDC	fixed-dose combination
FU	follow-up
GT	genotype
HCV	hepatitis C virus
HLGT	high level group term
HLT	high level term
ITT	intention-to-treat
INR	international normalized ratio of prothrombin time
LLOQ	lower limit of quantitation
LLT	lower level term
LSM	liver stiffness measurement
MedDRA	Medical Dictionary for Regulatory Activities
MELD	Model for End-Stage Liver Disease
mITT	modified intention-to-treat
mITT-VF	modified intention-to-treat, virological failure
PP	per-protocol
PT	preferred term
Q1	first quartile
Q3	third quartile
SAE	serious adverse event
SAP	statistical analysis plan
SD	standard deviation
SOC	system organ class
SVR	sustained virologic response
SVRx	sustained virologic response x weeks after stopping study drug
TD	target detected
TND	target not detected
ULN	upper limit of normal

## **INTRODUCTION**

The capacity to scale-up interferon-free DAA therapy would be enhanced by simplified treatment monitoring strategies. The “next generation” DAA regimen of glecaprevir/pibrentasvir, an NS3/4a protease inhibitor and an NS5A inhibitor, provide key features for HCV treatment simplification, including on-treatment monitoring: 1) pan-genotypic activity with very high efficacy (SVR>95%); 2) no relationship between time to undetectable HCV RNA and SVR; 3) minimal drug-related toxicity; 4) ease of dosing (three pills once daily); and 5) short duration (8 weeks for HCV treatment naïve individuals without cirrhosis; 12 weeks for HCV treatment naïve individuals with cirrhosis).

Current standard on-treatment monitoring in clinical trials involves clinic-based visits every 4 weeks. In the interferon-free DAA era with highly tolerable, effective and short duration therapy, this intensive monitoring strategy may no longer be required. A simplified on-treatment monitoring strategy is hypothesised to be non-inferior to the standard clinical trial on-treatment monitoring strategy. If successful, a simplified on-treatment monitoring strategy is likely to be highly attractive to patients, clinicians and health care payers. It has the potential to improve HCV treatment scale up, providing population level benefits in the reduction of global hepatitis C disease burden.

In people with chronic HCV (genotypes 1-6) who are treatment naïve and do not have cirrhosis, we hypothesise that the proportion achieving SVR following glecaprevir/pibrentasvir for 8 weeks with a simplified monitoring schedule will be non-inferior to glecaprevir/pibrentasvir for 8 weeks with a standard monitoring schedule.

This document describes the statistical analysis to be performed for the primary analysis of the SMART-C study, protocol version 2.0.

The analysis for the primary endpoint will be conducted after all participants complete the post-treatment Week 12 visit or prematurely discontinue from study. All the safety and efficacy data through to the post-treatment Week 12 visit will be cleaned, finalised, and included for the analysis. Prior to analyses, the study database will be locked in accordance with VHCRP Standard Operating Procedures and will have completed required quality assurance.

The primary analysis will focus on the non-inferiority of eight weeks of glecaprevir/pibrentasvir for treatment naïve patients without cirrhosis administered with simplified on-treatment monitoring strategy compared with a standard on-treatment monitoring strategy.

## STUDY DEFINITIONS

*Chronic HCV infection* is defined by detection of anti-HCV antibody and/or HCV RNA for greater than six months prior to screening.

*HCV virological suppression* is defined as HCV RNA below the lower limit of quantitation (LLOQ) (target not detected [TND] or target detected, not quantifiable [TDnq]).

An *end-of-treatment response (ETR)* is defined as HCV RNA below the LLOQ (TND or TDnq) at the end of treatment (date of treatment cessation).

HCV treatment outcome will be classified as:

- *Sustained virological response at 12 weeks post-treatment (SVR12)*: Defined as HCV RNA below the LLOQ (TND or TDnq) at 12 weeks post cessation of treatment.
- *Virologic failure*: Defined as HCV RNA above the LLOQ at 12 weeks post cessation of treatment (excluding reinfection).
  - In the **standard monitoring arm**, HCV virologic failure will be further defined as one of the following:
    - *Non-response* (failure of virological suppression on-treatment with quantifiable HCV RNA at all time points measured between baseline and end of treatment).
    - *Breakthrough* (an increase from non-quantifiable to quantifiable HCV RNA or to at least 1 log10 above nadir while on treatment).
    - *Post-treatment relapse* (the presence of quantifiable HCV RNA after end of treatment with detection of infection with an HCV strain consistent with the primary infecting strain, confirmed as homologous virus on sequencing).
- *Non-virologic failure*: Defined as death, premature treatment discontinuation, loss to follow up or missing plasma HCV RNA at post treatment week 12.
- *Reinfection*: Defined as HCV RNA above the LLOQ after end of treatment with detection of infection with an HCV strain that was distinct from the primary infecting strain, confirmed as heterologous virus on sequencing.

## STUDY OBJECTIVES AND DESIGN

### Study objectives

The *primary objective* of this study is:

- To compare the proportion of patients with undetectable HCV RNA (HCV RNA <LLOQ) at 12 weeks post-treatment (SVR12) following 8 weeks treatment with glecaprevir/pibrentasvir (300/120mg) in HCV treatment naïve non-cirrhosis chronic HCV patients who have received a standard versus simplified schedule of safety and virological monitoring (intention-to-treat population).

The *secondary objectives* of this study are:

- To compare the proportion of patients achieving SVR12 between those who received a standard versus simplified schedule of safety and virological monitoring, in the modified intention-to-treat population;
- To compare the proportion of patients achieving SVR12 between those who received a standard versus simplified schedule of safety and virological monitoring, in the per-protocol population;
- To evaluate the proportion adherent to treatment and study visits (on-treatment adherence and early treatment discontinuation);
- To evaluate patient reported outcomes following treatment;
- To evaluate safety and tolerability by monitoring adverse events during treatment;
- To evaluate patient treatment satisfaction;
- To evaluate the prevalence and impact of baseline resistance associated substitutions (RAS) on efficacy (SVR12);
- To evaluate cost-effectiveness of simplified monitoring;
- To evaluate immune-virological factors associated with SVR12.

The *exploratory objective* of this study is:

- To examine the provider acceptability of the simplified monitoring strategy.

Last dose of study drug refers to the last dose of glecaprevir/pibrentasvir and will be used in the definition of treatment-emergent adverse events and laboratory abnormalities, as well as the primary efficacy endpoint (SVR12).

### Study design

[figure not shown]
SMART-C is a Phase IIIb multicentre international randomised controlled trial. All participants will attend the study site for screening and baseline visits. Randomisation to study arm will occur at the baseline visit (**Figure 1**).

The two on-treatment monitoring strategies will differ as follows:

- Participants in the **standard monitoring arm** will have on-treatment study visits conducted at the site at weeks 4 and 8 (End of Treatment [EoT]).
- Participants in the **simplified monitoring arm** will have no on-treatment study visits conducted at the site.

Phone contact between the participant and site study nurse will occur in both arms 1-2 days prior to week 4 and week 8 (EoT) to provide standardized reporting of adverse events, concomitant medication and adherence.

One post treatment clinic visit will be conducted at post-treatment week 12 for all participants.

**Figure 1 Study Schema**

**Sample size and power**

The study was designed to enrol a total of 375 participants with genotype 1-6 HCV infection who had not received previous HCV treatment and did not have cirrhosis, randomised 2:1 - 250 participants in the simplified monitoring arm and 125 participants in the standard monitoring arm.

With these participant numbers and under the assumption that the proportion achieving SVR12 would be 96% in both arms, the study would have approximately 80% power to show non-inferiority of the simplified monitoring strategy to the standard monitoring strategy, with a lower confidence bound for SVR12 in the standard monitoring arm greater than 90% or with a lower confidence bound for the difference (simplified arm minus standard arm) in SVR12 greater than -6%. The 90% threshold for non-inferiority of the eight weeks glecaprevir/pibrenatasvir with standard monitoring was based on the clinical trial data available at the time of study design (SVR12 96%), minus a 6% non-inferiority margin. The non-inferiority margin of 6 percentage points was selected in accordance with the principles outlined in guidance on conducting non-inferiority trials; the choice of margin ensured minimal to no loss of efficacy.

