## **10.0 Statistics**

### **10.1 Sample Size**

The study is designed to enrol a total of 375 patients: 125 in the standard arm and 250 in the simplified arm. The primary efficacy endpoint of SVR12 will be assessed within each arm, and the primary comparison of SVR12 rates will be for non-inferiority of standard to simplified arms. With these patient numbers, the study has approximately 80% power to show non-inferiority to standard treatment monitoring with a lower confidence bound for the difference (standard – simplified) in SVR12 rates greater than –6% (assuming an SVR12 rate of 96% in both arms).

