## **GENERAL CONSIDERATIONS FOR DATA ANALYSES**

### **Statistical Methods**

Analysis results will be presented using descriptive statistics. For categorical variables, the number (n) and percentage of participants in each category will be presented. For continuous variables, the number of participants (n), mean and standard deviation (SD), median, interquartile range (IQR, Q1-Q3), range (minimum, maximum) will be reported; for inclusion in the manuscript, an appropriate determination will be made depending on the variable, size and distribution of the population studied. Statistical tests will be 2-sided and performed at the 5% significance level, unless specified. For the analysis of categorical outcomes, Chi-squared tests or exact equivalents (for small numbers) will be used. For comparison of continuous measures, t tests or non-parametric equivalents will be used as appropriate for the observed data distribution.

For the primary analysis of non-inferiority, the percentage of participants achieving SVR12 in each arm and the difference in percentages of participants achieving SVR12 between study arms will be calculated with confidence intervals using the normal approximation to the binomial distribution.

Non-inferiority of the 8-week regimen of glecaprevir/pibrentasvir with a simplified monitoring strategy to the 8-week regimen of glecaprevir/pibrentasvir with a standard monitoring strategy with regard to the proportion achieving SVR12 will be shown if the lower bound of the confidence interval for the differences is above the non-inferiority margin of -6 percentage points.

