## STUDY ENDPOINTS

**Table 9. Study endpoints and outcomes**

Primary endpoint	Non-inferiority of simplified on-treatment monitoring to standard on-treatment monitoring (ITT population)	Included in primary analysis
Secondary endpoints	Non-inferiority of simplified on-treatment monitoring to standard on-treatment monitoring (mITT population)	Included in primary analysis
	Non-inferiority of simplified on-treatment monitoring to standard on-treatment monitoring (per-protocol population)	Included in primary analysis
	Virologic failure	Included in primary analysis
	On-treatment adherence	Included in primary analysis
	Early treatment discontinuation	Included in primary analysis
	SVR12, by genotype	Included in primary analysis
	SVR12, by HIV serostatus	Included in primary analysis
	Adverse events	Included in primary analysis
	Laboratory abnormalities	Included in primary analysis
	Unscheduled clinic visits	Included in primary analysis
	Change from baseline in patient reported outcome summary measures	Included in primary analysis
	Presence of baseline polymorphisms	Included in primary analysis
	Presence of treatment-emergent substitutions in patients with virologic failure	Included in primary analysis
Additional pre-specified outcomes	Cost-effectiveness	Not included in primary analysis
	Health practitioner acceptability	Included in primary analysis

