### Primary efficacy endpoint

The primary efficacy endpoint is sustained virologic response at week 12 post treatment (SVR12), defined as plasma HCV RNA below the lower limit of quantitation (<10 IU/mL; target not detected [TND] or target detected, not quantifiable [TDnq]) at 12 weeks after the last dose of study drug in the ITT population.

The Aptima HCV Quant Dx assay, version 2.15.5 will be used to measure HCV RNA (Hologic, Inc., Marlborough, MA, USA). The LLOQ for this assay is 10 IU/mL.

The primary efficacy endpoint of SVR12 will be assessed within each arm, and the primary comparison of SVR12 will be for non-inferiority of the simplified monitoring arm compared to the standard monitoring arm (simplified arm minus standard arm).

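### The primary non-inferiority criterion is worded in conflicting ways: the SAP sample-size section adds a standard-arm-only route, and protocol 10.1 reverses the contrast

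*SAP*

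**What the plan says.** **The rule as intended.** The hypothesis (protocol synopsis and 2.1) is that simplified monitoring is non-inferior to standard in the ITT population. SAP Statistical Methods declares this if "the lower bound of the confidence interval for the differences is above the non-inferiority margin of -6 percentage points". SAP Primary efficacy endpoint fixes the order of subtraction as simplified minus standard, and SAP Table 9 names the endpoint in the same direction. None of these three SAP places mentions a 90% threshold.

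**Text that does not match.**

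- SAP, Sample size and power: non-inferiority of simplified to standard is to be shown "with a lower confidence bound for SVR12 in the standard monitoring arm greater than 90% or with a lower confidence bound for the difference" (simplified minus standard) above -6%. The following sentence explains "The 90% threshold for non-inferiority of the eight weeks glecaprevir/pibrenatasvir with standard monitoring" as the 96% seen in earlier trials less the 6-point margin.
- Protocol 10.1: "the primary comparison of SVR12 rates will be for non-inferiority of standard to simplified arms", with a "lower confidence bound for the difference (standard – simplified) in SVR12 rates greater than" -6%. The sentence that holds this reversed contrast nevertheless claims "approximately 80% power to show non-inferiority to standard treatment monitoring".
- Protocol 10.3: the arms count as non-inferior if the lower 95% limit of the between-arm difference does not exceed -6%. No order of subtraction is given.

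**The concern.** This is the trial's one primary decision criterion, and the mismatches are of substance.

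- The standard-arm clause asks whether the regimen under standard monitoring holds up against earlier trials. That is a legitimate question, but its answer carries no information about the simplified arm. Joined by an *or* to the claim about simplified monitoring, it would allow success however badly that arm performed.
- The reversed contrast in protocol 10.1 protects against the standard arm being worse than the simplified arm, which is not the risk the trial was set up to exclude.
- The wording in protocol 10.3, taken literally, rewards a lower limit at or below the margin.

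No text says which wording prevails. If the result falls where the wordings disagree, the criterion could be disputed after the data are known.

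**Working it through.** **Inputs.** 125 standard and 250 simplified; SVR12 of 96% in both arms; margin 6 points; power of approximately 80% (protocol 10.1; SAP Sample size and power). Confidence limits by the normal approximation, and tests two-sided at 5% (SAP Statistical Methods). The 95% level is stated in protocol 10.3.

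**Step 1: reproduce the stated power.** For the difference rule alone:

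SE = √[0.96 × 0.04 × (1/125 + 1/250)] = 0.02147

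Power = Φ(0.06/0.02147 − 1.96) = Φ(0.835) = 79.8%

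This agrees with the stated figure. A two-sided 90% interval would give 87.5%, so the calculation rests on a two-sided 95% interval. Because the assumed rates are equal, the formula gives the same power for either order of subtraction, so the power figure cannot reveal the reversal in protocol 10.1.

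**Step 2: what the standard-arm clause requires.** The lower limit is p − 1.96 × √[p(1 − p)/125]. At 117/125 it is 0.893 and at 118/125 it is 0.904, so 118 or more responders satisfy it. At a true rate of 96% that happens with probability 87.1%, whatever occurs in the simplified arm. With an exact (Clopper-Pearson) limit the requirement is 120 or more, and the probability is 61.6%.

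**Step 3: probability of declaring non-inferiority under each wording.** All pairs of responder counts (0 to 125, 0 to 250) were enumerated with exact binomial probabilities, applying 95% normal-approximation limits to each pair. Figures in brackets use the exact limit for the standard-arm clause.

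| True SVR12, standard / simplified | Simplified minus standard (SAP Statistical Methods with Primary efficacy endpoint) | Two-route wording (SAP Sample size and power) | Standard minus simplified (protocol 10.1) |
|---|---|---|---|
| 96% / 96% | 83.3% | 99.9% (99.0%) | 78.2% |
| 96% / 93% | 23.2% | 95.3% (78.9%) | 94.8% |
| 96% / 90% | 2.1% | 88.5% (63.6%) | 99.2% |
| 96% / 85% | below 0.1% | 87.1% (61.6%) | above 99.9% |

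The literal reading of protocol 10.3, taken as simplified minus standard, would succeed 16.7% of the time at 96%/96% and 97.9% at 96%/90%. The stated power therefore excludes it as the intended meaning. The two-route wording, at 99.9%, does not match the stated power either.

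**Step 4: one possible result.** Suppose 120/125 (96.0%) against 230/250 (92.0%).

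SE = √(0.96 × 0.04/125 + 0.92 × 0.08/250) = 0.02453

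Simplified minus standard = −4.0 points, 95% CI −8.8 to +0.8

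- Difference rule: −8.8 is below −6, so non-inferiority is not shown.
- Standard-arm clause: 0.96 − 1.96 × 0.01753 = 92.6%, above 90%, so it is met.
- Reversed contrast: the lower limit is −0.8, above −6, so it is met.

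**The case against.** The strongest reply is that the operative rule is not really in doubt. Only SAP Statistical Methods says when non-inferiority will be concluded, and it has no 90% clause. The other SAP text and protocol 10.1 are statements about power. The SAP sample-size section also contains the correct contrast and margin as its second route. Both documents say SVR12 will be assessed within each arm, which gives the 90% figure a natural place as a within-arm benchmark. Protocol 10.2 defers to a final SAP, signed off before data lock.

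Much of this stands. An analyst following the SAP would probably apply the right rule, and the large probabilities above arise only if another wording is applied in its place. The bracketed exact-limit figures depart from the normal approximation specified for the primary analysis. The 96%/93% row is an assumed scenario: the documents report 93.1% for genotypes 4–6, but nothing suggests that monitoring would produce such a gap between arms. The missing 95% level and order of subtraction in SAP Statistical Methods can be recovered from other sections, so adding them there is editorial.

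The reply does not remove the conflict. Deferring to a SAP cannot settle a disagreement inside the SAP. The SAP also describes itself as following protocol version 2.0, whose statistics section gives only one signed contrast, and that one is reversed.

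**Conclusion.** The concern holds. The primary criterion is correct where SAP Statistical Methods and Primary efficacy endpoint are combined. It is wrong as written in the SAP sample-size section and in protocol 10.1, and wrong if read literally in protocol 10.3. When simplified monitoring is truly 6 points worse (96% against 90%), the chance of declaring non-inferiority moves from 2.1% to 88.5% or 99.2% depending on which of the first three wordings is used. These figures assume the planned 125 and 250 participants, independent binomial outcomes and two-sided 95% normal-approximation limits. They describe what each wording would do if applied, not how likely it is to be applied. The sample size, the stated power and the intended analysis are not in question. The defect should be fixed before the data are analysed.

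**What to change.** State one rule in both documents: simplified monitoring is non-inferior if the lower limit of the two-sided 95% confidence interval for the difference in SVR12, simplified minus standard, in the ITT population, is greater than -6 percentage points.

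- SAP, Sample size and power: delete the 90% standard-arm clause, or relabel it as a descriptive within-arm benchmark with no part in the non-inferiority claim.
- Protocol 10.1: name the comparison as simplified against standard and reverse the subtraction.
- Protocol 10.3: require the lower limit to be greater than -6%, and give the order of subtraction.
- SAP Statistical Methods: add the 95% level and the order of subtraction, for completeness.

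These are wording changes. They need no new data, participants or recalculation, and sample size and power stay as they are. The protocol edits count as an amendment, for which protocol 13.0 requires ethics approval at each site. If that is disproportionate, correcting the SAP and adding a sentence that its decision rule governs over protocol 10.1 and 10.3 would resolve the ambiguity. Either should be done before data lock.
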